6.4 Replacement of dropouts

A minimum of 3 patients per cohort/sub-cohort are required to complete the entirety of Cycle 1 (including the applicable treatment and rest periods). Contingent on the number of prior DLTs within a cohort/sub-cohort, non-completers of Cycle 1 will be replaced to ensure a minimum of 3 patients complete Cycle 1 of each cohort/sub-cohort.

CC

CCI

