12.5 Safety and Tolerability Data

Demographics will be tabulated and summarized. Medical and surgical history data at Screening will be listed, as will Physical Examination data (including height and weight) at Screening, and at subsequent visits. All characteristics at Baseline such as age, weight, height, vital signs (resting heart rate, semi-supine systolic/diastolic blood pressure, respiratory rate and temperature), and ECG parameters will be tabulated and summarized.

All patients receiving at least one dose of IMG-7289 will be included in the safety analysis.

Laboratory values outside the laboratory normal ranges will be summarized and assessed for change from Day 1 and trends indicating a safety signal.

Treatment-emergent adverse events will be coded using the most updated version of Medical Dictionary for Regulatory Activities (MedDRA) available to the Sponsor at the time of study initiation (up-versioning will not occur) and summarized by cohort for the number of patients reporting the AE and the number of AEs reported. A by-patient AE data listing including (but not limited to) verbatim term, coded term, cohort, severity, and relationship to treatment will be provided.

Concomitant medications will be listed by patient and coded using the most updated version of WHO drug dictionary available to the Sponsor at the time of study initiation (up-versioning will not occur). Medical history will be listed by patient.

Descriptive statistics (arithmetic mean, standard deviation (SD), sample size, CV (coefficient of variation), median, minimum, maximum, and number) will be calculated for quantitative safety data as well as for the differences to baseline, when appropriate. In addition, a shift table describing out of normal range shifts will be provided for clinical laboratory results, and ECG tracings. Chi-square (χ^2), Fisher exact, and Kruskal-Wallis tests may be used to assess the significance of differences in baseline patient characteristics. For safety and tolerability, missing data including those not obtained because of death will be the last value carried forward.

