The protocol (Section 4.1) lists the following hypothesis: IMG-7289 with and without all-*trans* retinoic acid (ATRA; tretinoin) is a safe and tolerable orally available agent when administered to patients with advanced myeloid malignancies including high risk AML and high risk MDS; LSDi by IMG-7289 will have a negative impact on leukaemic and dysplastic cells, an effect which may be further enhanced *via* synergistic mechanisms when administered in combination with ATRA.

B. Primary

The protocol (Section 4.2) lists the following primary objectives:

- Safety and tolerability
- Pharmacokinetics
- The adequacy of dose and duration in producing a pharmacodynamic effect

C. Secondary

The protocol (Section 4.2) lists the following secondary objectives:

- The association of plasma concentrations (C_{\max} and C_{\min}) and exposure (AUC) on haematopoiesis (both short and longer-term measures)
- The kinetics of recovery of haematopoiesis for a given dose and for a given duration of dosing

CCI

III. Study Endpoints

A. Primary

[figure not shown]
The safety and tolerability of IMG-7289 with and without ATRA will be assessed by the analysis of adverse events (AEs), as well as changes in physical examinations, vital signs and laboratory values as detailed below.

- Monitoring of Adverse Events (AEs) including determination of dose limiting toxicities (DLTs), medical events of interest (MEOIs), serious adverse events (SAEs), and AEs. AEs will be assessed in terms of onset, duration, seriousness, severity, and causality, using the National Cancer Institute Common Terminology Criteria for Adverse Events (NCI CTCAE), Version 4.03. Deaths and other serious adverse events (SAEs) will also be evaluated and will be collected on a separate case report form (CRF).
- Changes in physical examinations, vital signs and laboratory values will also be evaluated and assessed. Information on the timing of these assessments is presented in Protocol Section 9. The following laboratory tests will be conducted:
 - Complete blood counts (CBC) and differential
 - Coagulation
 - Chemistry panel including LFTs (AST, ALT, INR, total bilirubin, gamma glutamyltransferase (GGT), and albumin)
 - Urinalysis with microscopy
 - Electrocardiograms

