- Therapies that are not marked as ongoing, and have a stop date with a missing day and month will be assumed to occur on the *last* day of the non-missing year (i.e. December 31).

For the listings, AE, CM and PCTHX dates will be listed as collected in the eCRF. All other data will be reported as they are collected. No imputation methods will be used to replace missing data unless otherwise stated in this document.

Partial transfusion start dates are not permitted, and thus assumptions should not be needed to determine if the transfusion was prior to the first dose of IMG-7289.

E. Multiple Study Centers

There will be no adjustment for multiple study centers in the analysis.

F. Covariate Adjustment in Primary Analysis

There will be no adjustment in the analysis for covariates.

G. Sample Size Reassessment

No sample size reassessment is planned for this study.

H. Interim Analyses or Timing of Analyses

The Data Safety Monitoring Committee (DSMC) will review safety parameters, pharmacodynamic markers, and pharmacokinetic parameters to draw conclusions around the safety and pharmacodynamic effect of differing doses, treatment regimens and dosing durations. DSMC reviews are critical, as neither a new dose-finding sub-cohort, nor a duration-finding cohort may commence without DSMC review and recommendation to do so. Refer to Protocol Section 8 for details pertaining to DSMC reviews, and management of study toxicities.

I. Multiple Comparisons

No control for the effect of multiple comparisons is planned.

J. Analysis Populations

Two analysis populations will be defined for use with various analyses.

1. Safety Population

All enrolled patients who received at least one dose of IMG-7289 will be included in the Safety population.

2. Efficacy Population

All enrolled patients who received at least one dose of IMG-7289 and have disease assessment at baseline (Bone Marrow Aspirate/Biopsy and Haematology). Patients having no post-baseline response assessment will be defined as NE (Not Evaluable).

K. Data Display Characteristics

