Additionally, the Kaplan-Meier method will be used to analyze event-free survival (EFS) and overall survival (OS); Summaries will present the number (%) of subjects with events, the number (%) of subjects without events (censored), the median (95% CI) survival, and the probability of 6-month survival. OS is defined as the time interval between treatment start date and death date, and OS will be censored at the last date known alive. EFS is defined as the time interval between the date of treatment start and date of resistance, relapse, progression, or death. For subjects that do not have an event, EFS will be censored at the date of last tumor assessment prior to any concurrent cancer chemotherapy and transfusion.

IX. Safety Analysis

The safety and tolerability of IMG-7289 with and without ATRA will be assessed by the analysis of adverse events (AEs), as well as changes in physical examinations, vital signs, laboratory values and ECGs as detailed below, using the Safety Population.

A. Adverse Events

The AEs reported on the eCRFs will be coded using the latest version of MedDRA available to the sponsor at the time of study initiation (up-versioning will not occur), associating lower-level terms with preferred terms and system organ classes (SOC) by the primary hierarchy. The tables will display counts and percentages of subjects who reported at least one AE in each system organ class represented in the AE data. Within each system organ class, the tables will display the counts and percentages of subjects reporting at least one AE, as designated by the preferred terms.

In any given category (e.g., SOC or preferred term) a patient will be counted only once. If a patient has the same AE on multiple occasions, only the highest toxicity grade will be used. Similarly, only the most related event will be used. Percentages will be based on the number of patients in the subgroup of patients being tabulated and not the number of events. Summaries that are displayed by system organ class and preferred terms will be ordered by descending order of incidence of system organ class and preferred term within each system organ class.

Treatment-emergent adverse events will be summarized. Only those events with an onset date on or after the date on which IMG-7289 was first dispensed, and within 28 days of last IMG-7289 treatment are to be recorded on the AE eCRF; therefore, all reported AEs are expected to be treatment-emergent. However, if eCRF completion

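### The SAP has no DLT-evaluable population, so a DLT rate reported on all dosed patients is too low in any cohort where a Cycle 1 non-completer without a DLT was replaced

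*SAP*

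**What the plan says.** SAP VI.J (Analysis Populations) opens with "Two analysis populations will be defined for use with various analyses". For the first it says: "All enrolled patients who received at least one dose of IMG-7289 will be included in the Safety population". The second, the Efficacy population, adds only a requirement for a baseline marrow and haematology assessment. Neither depends on finishing Cycle 1 or on DLT status.

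SAP IX (Safety Analysis) covers adverse events together with "vital signs, laboratory values and ECGs as detailed below, using the Safety Population". Protocol 12.5 agrees: "All patients receiving at least one dose of IMG-7289 will be included in the safety analysis". DLTs fall under this heading, because SAP III.A (matching protocol 12.4.1) lists within the primary safety endpoint "Monitoring of Adverse Events (AEs) including determination of dose limiting toxicities (DLTs), medical events of interest (MEOIs), serious adverse events (SAEs), and AEs". SAP IX.A takes adverse-event percentages over the patients in the group being tabulated.

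The protocol limits DLTs to the first cycle (8.2.1). Section 6.4 provides, contingent on the number of earlier DLTs, that "non-completers of Cycle 1 will be replaced to ensure a minimum of 3 patients complete Cycle 1 of each cohort/sub-cohort". The DSMC reviews each cohort once at least three patients have finished Cycle 1, and the rule in 8.2.2 (Table 5) and the MTD definition in 8.2.3 are both written in terms of three patients.

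**The concern.** A patient who stops partway through Cycle 1 without a DLT has been watched for only part of the window in which a DLT can count. The protocol brings in another patient so that three are followed to the end. The SAP has no matching population. Under its stated rule, the patient who left stays in the denominator as though fully observed and DLT-free.

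The reported DLT rate for a dose, duration or combination would then be lower than the rate among patients observed through the window. With cohorts as small as three, one such patient visibly changes the percentage and its confidence limit.

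The effect could also differ between cohorts. From protocol Tables 1 and 4, Cycle 1 lasts 7 + 7 = 14 days in Cohort 1, 14 + 7 = 21 days in Cohorts 3/3χ and 21 + 7 = 28 days in Cohorts 4/4χ. A longer window leaves more time for departures unrelated to study drug, so dilution could be greater in the longer-duration cohorts. The documents do not show whether it would be.

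**Working it through.** The documents give no DLT rate, no DLT target and no Cycle 1 non-completion rate, so there is no planned figure to reproduce. The check shows what the population rule does to a small-cohort proportion.

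**Inputs**
- Minimum of three Cycle 1 completers per cohort or sub-cohort: protocol 6.4.
- Denominator for safety analyses is all dosed patients: SAP VI.J and IX; protocol 12.5.
- DLT window is Cycle 1: protocol 8.2.1.
- Number of replaced patients without a DLT, *r*: not given. Assumed to be 0 to 3.

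**Formulas.** Take *x* DLTs among three evaluable patients, where evaluable means having had a Cycle 1 DLT or having completed Cycle 1.
- Evaluable rate = x/3.
- All-dosed rate = x/(3 + r), because each replaced DLT-free patient adds 1 to the denominator and 0 to the numerator.
- Exact (Clopper-Pearson) 95% limits for x of n: the lower is the 2.5% quantile of Beta(x, n − x + 1), and the upper is the 97.5% quantile of Beta(x + 1, n − x). For x = 0 the lower limit is 0 and the upper limit is 1 − 0.025^(1/n).

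**Results: rate (exact 95% limits)**

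| DLTs | r = 0 (n = 3) | r = 1 (n = 4) | r = 2 (n = 5) | r = 3 (n = 6) |
|---|---|---|---|---|
| 0 | 0% (0–70.8) | 0% (0–60.2) | 0% (0–52.2) | 0% (0–45.9) |
| 1 | 33.3% (0.8–90.6) | 25.0% (0.6–80.6) | 20.0% (0.5–71.6) | 16.7% (0.4–64.1) |
| 2 | 66.7% (9.4–99.2) | 50.0% (6.8–93.2) | 40.0% (5.3–85.3) | 33.3% (4.3–77.7) |

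The second and third rows show the rate itself falling. In the first row the rate cannot fall, but the upper limit does, so a cohort without DLTs looks better bounded than its fully observed patients justify. In the last row, a cohort that met the stopping threshold of two in three would be tabulated at 50.0% after one replacement.

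**General form.** If *d* is the share of dosed patients who left Cycle 1 without a DLT, the all-dosed rate equals the evaluable rate × (1 − d). For an evaluable rate of 33.3% and assumed values of d of 10%, 20%, 30% and 40%, it is 30.0%, 26.7%, 23.3% and 20.0%.

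**Could another summary repair this?** The disposition table in SAP VII.B counts completion of all the initially allowed cycles (four in Cohort 1), not completion of Cycle 1. A reader would have to rebuild the evaluable denominator from patient listings.

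**The case against.** The strongest objection is that no visible text plans a DLT percentage. The passage following severity grading in SAP IX.A is blacked out, most of protocol 8.2.2 is too, and display details are left to shells that are not in the documents. A DLT table with its own denominator could exist there. This stands as a limit on certainty. It does not remove the point, because VI.J is fully legible and offers no population on which such a table could be built.

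A second objection is that the all-dosed rate is a legitimate crude incidence, while the evaluable set has its own bias: it keeps every early DLT but drops a patient who left DLT-free, even one day before the window closed. If leaving is unrelated to DLT risk, the evaluable rate errs high and the all-dosed rate errs low. This is right, and it is why both rates should be shown.

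Third, the intervals are very wide on either denominator, and patient-level listings allow individual cases to be checked. That also stands, and it limits the practical weight of the point.

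A reader might infer more than the documents support:
- *That escalation or the MTD is distorted.* These follow the DSMC rule, not a SAP percentage.
- *That the DSMC decides on completers alone.* Three completers is the minimum that triggers review. Patients with a DLT may themselves be replaced, and the DSMC may stop escalation with fewer than two DLTs.
- *That reported DLT counts will disagree with those the DSMC saw.* The choice of population leaves the numerator unchanged.
- *That every DLT rate is understated by a fixed fraction.* Only patients who leave without a DLT dilute a rate, only in cohorts that have such patients, and a rate of zero stays zero. Any assumed share, such as 20–40%, has no source in the documents.

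**Conclusion.** The point holds as a reporting gap in a component of the primary endpoint. Under the stated population rule, a nonzero DLT rate is lower than the rate among patients observed through Cycle 1 whenever a patient leaves that cycle without a DLT and is replaced. For one DLT in three evaluable patients, the drop is 8.3 percentage points with one replacement (33.3 − 25.0) and 13.3 with two (33.3 − 20.0). For no DLTs, the upper limit drops by 10.6 points with one replacement (70.8 − 60.2).

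These sizes assume exactly three evaluable patients and one or two replacements. A cohort with no DLT-free departures is unaffected, and how many cohorts will have them cannot be known from the documents. The conclusion also assumes that the blacked-out part of SAP IX.A does not set a separate DLT denominator. It is worth correcting before database lock, but no decision about a patient or a dose turns on it.

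**What to change.** Add a third population to SAP VI.J: DLT-evaluable, meaning Safety Population patients who either had a DLT in Cycle 1 or completed both the dosing and rest periods of Cycle 1. Tabulate DLTs on this set by cohort and sub-cohort with exact 95% confidence intervals, and show the all-dosed rate beside it. List the patients excluded from the set with their reasons. Keep the Safety Population for all other adverse-event tables.

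The cost is one SAP paragraph, one flag and one table, using data already collected. SAP I.B allows changes until database lock. DLT percentages will look slightly less favourable in affected cohorts, and the evaluable rate may somewhat overstate risk because it omits patients who left DLT-free. Showing both denominators lets the reader see the range.

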6.7 Patients Who Terminate Early or Discontinue Study Medication

All patients who finish the study early, or who discontinue study medication will be requested to return for follow-up visits, beginning with an End of Treatment visit as detailed in Section 9.12.1. If a patient refuses to enter follow up, perform an Early Termination visit as detailed in Section 9.12.3 Patients who discontinue study medication due to a DLT will be asked to continue follow-up.

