The intended dosing plan for high risk AML/MDS patients is predicated on the supposition that LSD1 must be maximally inhibited to achieve the greatest therapeutic benefit. The concentrations of LSD1 inhibitors such as IMG-7289 (free base) used to achieve maximal effects on growth, differentiation and apoptosis *in vitro* with primary patient-derived AML cells as well as AML cell lines are similar to concentrations that *in vivo* inhibit red cell, platelet and granulocyte production. It is therefore expected that high risk AML/MDS patients will require treatment at doses sufficient to induce profound thrombocytopenia and neutropenia. These drug-induced but reversible cytopenias can be managed clinically as needed with platelet and red cell transfusions as well as broad-spectrum antibiotics in the case of febrile neutropenia, as are already standard practices in the routine management of AML/MDS patients receiving intensive SOC chemotherapy.

The effects of IMG-7289 on normal myeloid haematopoiesis observed in non-clinical studies are expected in humans; these are pharmacodynamic effects of LSD1 inhibition by IMG-7289, thus are not regarded as adverse. These events, with the exceptions noted below, will not be considered DLTs.

Dose Limiting Toxicity (DLT): DLT is defined as any one of the following AEs that occurs during the first cycle of therapy and is considered by the Investigator to be possibly, probably or definitely related to IMG-7289.

- A clinically significant bleeding event;
- Any Grade 4 or 5 non-haematologic adverse event;

- Any Grade 3 non-haematologic adverse event with failure to recover to Grade 1 within 7 days of drug cessation, with the following exceptions:
 - ≥ Grade 3 nausea, vomiting or diarrhoea that responds to standard medical care
 - ≥ Grade 3 aesthenia lasting less than 14 days
- Any Grade 3 electrolyte abnormality unrelated to the underlying malignancy and persisting greater than 24 hours.

Patients who experience a dose limiting toxicity (DLT) will have their dose adjusted downward if the Medical Monitor and Principal Investigator deem it safe for the patient to continue on IMG-7289. To ensure a minimum of 3 Cycle 1 completers, and contingent on the number of prior DLTs within the sub-cohort/cohort, such patients may be replaced.

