Any patient that experiences a DLT that results in discontinuation of IMG-7289 therapy may begin alternative therapy after a one week washout period and if their physician deems this safe and appropriate regarding the resolution of the DLT.

Please consult the Medical Monitor for IMG-7289 dose modifications for the management of clinically significant changes in platelets, neutrophil counts, or other haematologic parameters.

Expected toxicities based on non-clinical studies with IMG-7289 are reported in the latest edition of the Investigator's Brochure.

CCI

CCI

Additionally, the DSMC may review safety data and, even in the absence of 2 DLTs, deem that the safe dose has been exceeded. Were this to occur, dose escalation would cease.

Table 5: IMG-7289 Dose Limiting Toxicity and Escalation Decision*

Patients with DLT at a Given Dose	Escalation Decision Rules
0-1 out of 3	Open subsequent sub-cohort/next dose
2 out of 3	Dose escalation will be stopped

*The above instruction applies in kind for combination therapy and duration extension decision making.

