The primary objective, the adequacy of IMG-7289 dose and duration with and without ATRA in producing a pharmacodynamic effect, will be determined using serial blood and bone marrow sampling throughout the course of treatment with responses documented according to revised/modified International Working Group (IWG) Response Criteria – [Cheson *et al.* 2003](#) for AML and [Cheson *et al.* 2006](#) for MDS as described in Protocol Section 16.2. Response is to be assessed each time a bone marrow aspirate or biopsy is performed, with the exception of baseline. All available response data will be listed. The visit overall response per patient, as determined by the Investigator, and recorded on the eCRF, will be listed and summarized for each cohort, using the Efficacy Population.

The best response of each AML patient will be programmatically selected based on the following order: Complete Remission (CR), CR w/Incomplete Recovery (CRi), Morphologic Leukaemia-Free State (MLFS), Partial Remission (PR), Cytogenetic CR (CRc), Molecular CR (CRm), Stable Disease (SD), Resistant Disease (RD), Relapse (Rel), Progressive Disease (PD), Death from Indeterminate Cause (DInd), Death in Aplasia (DiA), and Not Evaluable. The best response of each MDS patient will be programmatically selected based on the following order: Complete Remission (CR), Partial Remission (PR), Marrow CR (CRm), Cytogenetic Response (CyR), Stable Disease (SD), Relapse After CR or PR (Rel), Disease Progression (DP), Failure: Disease Progression (FDP), Survival (Sur), Failure: Death During Treatment (FDDT), and Not Evaluable.

Objective response in AML includes Complete remission (CR), CR with incomplete recovery (CRi), Morphologic leukemia-free state, Partial remission (PR), Cytogenetic CR (CRc), and Molecular CR (CRm) and Stable Disease (SD); while objective response in MDS includes Complete remission (CR), Partial remission (PR), Marrow CR, or Cytogenetic response (CyR) and Stable Disease (SD). Objective response rate (ORR) is the proportion of responders with AML or MDS. ORR and its Fisher exact 95% confidence interval will be presented.

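### AML best response has no cut-off at new anticancer therapy, so after a Cycle 1 DLT a response to the next treatment could be credited to IMG-7289

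*SAP*

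**What the plan says.** SAP VIII.A ties response to the primary objective on adequacy of dose and duration, which "will be determined using serial blood and bone marrow sampling throughout the course of treatment with responses documented" by IWG criteria. On timing it says: "Response is to be assessed each time a bone marrow aspirate or biopsy is performed, with the exception of baseline". On selection: "The best response of each AML patient will be programmatically selected based on the following order", starting with CR and running down to not evaluable. Objective response in AML covers everything from CR to stable disease (SD), including MLFS. The same section does stop at new treatment for patients without an EFS event: "EFS will be censored at the date of last tumor assessment prior to any concurrent cancer chemotherapy and transfusion".

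The Efficacy Population (SAP VI.J) is "All enrolled patients who received at least one dose of IMG-7289 and have disease assessment at baseline", so stopping early does not remove a patient.

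Protocol 16.1.1 schedules a marrow at End of Treatment (EOT) and at EOS. Section 5.1 puts these visits about 7 and 28 days after last dose. Protocol 8.2.1 states: "Any patient that experiences a DLT that results in discontinuation of IMG-7289 therapy may begin alternative therapy after a one week washout period", with the further condition that the physician finds this safe and appropriate given how the DLT has resolved. Section 6.7 adds: "Patients who discontinue study medication due to a DLT will be asked to continue follow-up". Section 11 says that patients withdrawn for a DLT should undergo all follow-up procedures.

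**The concern.** Best response is chosen by rank, whatever the order in time, and baseline is the only assessment left out. A patient can stop IMG-7289, start another drug, and have the EOS marrow while on that drug. If that marrow shows MLFS or better, the program selects it as the response to IMG-7289. A patient recorded as resistant at EOT and MLFS at EOS would then be both an EFS event and an objective responder for the IMG-7289 cohort.

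Any such error can only raise ORR, and response is how the SAP documents a primary objective. Cohorts may be as small as 3, so a single case is conspicuous.

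**Working it through.** **1. Is the EOS marrow really in the data?** Protocol section 10 states 4 marrow samples for Cohort 1 and 3 each for Cohorts 3/3χ and 4/4χ, through EOS. Counting from the schedule, with EOT replacing the last rest-day visit for a patient who is finishing:
- Cohort 1: baseline, Cycle 2 Day 14, Cycle 4 Day 14/EOT, EOS = 4
- Cohort 3/3χ: baseline, Cycle 2 Day 21/EOT, EOS = 3
- Cohort 4/4χ: baseline, Cycle 1 Day 28/EOT, EOS = 3

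The stated counts are reproduced only with EOS included.

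**2. Longest time on new therapy before EOS.** 28 − 7 = 21 days, for a patient who starts as soon as the one-week washout ends.

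**3. Could a DLT patient already count through SD?** The window is fixed: "DLT is defined as any one of the following AEs that occurs during the first cycle of therapy". On the standard schedule, the last Cycle 1 dose is by Day 7, 14 or 21. EOS is therefore by Day 7 + 28 = 35, 14 + 28 = 42 or 21 + 28 = 49. Table 14 requires more than 8 weeks (56 days) for SD. A patient who stops in Cycle 1 cannot reach SD by EOS, so a new MLFS would change ORR.

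**4. Can one marrow establish a response?** In AML, yes. MLFS needs no count recovery and Table 14 gives it no duration; its footnote requires no minimum duration for CR. In MDS, no: Table 15 requires responses to last at least 4 weeks (28 days), and at most 21 days are available.

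**5. Effect of one case on ORR** (Clopper-Pearson, taken as the meaning of the SAP's Fisher exact interval):

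| Without the case | With the case |
|---|---|
| 0/3 = 0% (0 to 70.8%) | 1/3 = 33.3% (0.8 to 90.6%) |
| 1/3 = 33.3% (0.8 to 90.6%) | 2/3 = 66.7% (9.4 to 99.2%) |
| 8/40 = 20.0% (9.1 to 35.6%) | 9/40 = 22.5% (10.8 to 38.5%) |

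In 40 patients each case adds 1/40 = 2.5 points. The 8/40 starting point is illustrative.

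**6. How many cases?** The documents give no AML share, DLT rate or rate of subsequent therapy, so every input here is assumed. Formula: AML patients × share exposed × share reaching MLFS or better by EOS.
- DLT discontinuations only (20 AML patients, 5–15% exposed, 5–20% responding): 20 × 0.05 × 0.05 = 0.05 to 20 × 0.15 × 0.20 = 0.6 patients, or 0.125 to 1.5 points of 40.
- Any patient starting new therapy before EOS (20 AML patients, 10–30% exposed, 5–20% responding): 20 × 0.10 × 0.05 = 0.1 to 20 × 0.30 × 0.20 = 1.2 patients, or 0.25 to 3 points. With 10 AML patients this is 0.05 to 0.6; with 30 it is 0.15 to 1.8.

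All of these are upper bounds. The first assumes that every DLT discontinuation starts new therapy before EOS and has the EOS marrow. The second also ignores that a patient with earlier SD or better cannot be added to ORR, and it assumes that no unseen text bars the therapy.

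**The case against.** The strongest reply has four parts.

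*The SAP refers to the course of treatment, and EOS is a follow-up visit.* That phrase describes the sampling. The next sentence covers every marrow except baseline, and no analysis window is defined. If follow-up marrows are meant to be excluded, one sentence would settle it.

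*The DLT route is narrow.* This stands. The permission depends on the physician's view of DLT resolution. One DLT category is a Grade 3 event not recovered to Grade 1 within 7 days, which fits poorly with a Day 7 start, and a Grade 5 DLT is a death. The patient must also have AML, return for EOS and respond within about three weeks. The eligible AML population is largely unfit for, or out of, standard options.

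*Investigators determine the visit response and might not credit another drug's effect.* Possible, but no visible text tells them not to, and best response is programmed from what they record. Listings of responses and of chemotherapy let a reader trace a case; they do not correct ORR.

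*Little hangs on ORR.* This also stands. ORR has no threshold, the sample size rests on safety and pharmacokinetics, and the DSMC review that governs escalation follows Cycle 1.

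A reader might infer that any patient may start new therapy a week after last dose. The documents do not support that. Inclusion criterion 9 records willingness to stay off other anti-neoplastic treatment until one week after last dose; it does not grant permission afterwards. Sections 6.6 and 9.12 are redacted and may bar it. Section 6.3 makes taking another investigational agent a possible reason for removal.

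**Conclusion.** The concern holds in a limited form, as a minor point. On the visible text, the AML rule can credit IMG-7289 with a response achieved on another drug, and the SAP already uses a new-therapy cut-off for EFS censoring. Clear exposure is confined to AML patients who discontinue for a Cycle 1 DLT and whose physician judges alternative therapy safe before EOS. For other AML patients exposure is only an inference.

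One case is worth 33.3 points in a cohort of 3 and 2.5 points in 40. The number of cases is unknown and probably low; the counts above, including 0.05 to 0.6 for the DLT route, are upper bounds on assumed inputs. It would go too far to conclude that ORR will be materially inflated, that MDS response is affected in the same way, or that dose selection is compromised. The documents give no rates to support the first, Table 15's duration requirement guards against the second, and escalation does not use ORR.

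**What to change.** In SAP VIII.A, state that best response and ORR are derived only from assessments dated on or before the start of any new anticancer therapy. Count transplant conditioning as new therapy; do not count permitted hydroxyurea, study ATRA or transfusions. List later assessments separately.

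Query partial start dates of post-treatment therapy instead of applying SAP VI.D. The eCRF requires only the year, and a year-only start in the first year of dosing is imputed to the first day of dosing. Under the new rule that would discard every post-baseline marrow for the patient.

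The cost is one sentence plus a few date queries, and the SAP can be modified until database lock. The EOT marrow, at about Day 7, is normally kept. A patient who starts new therapy between then and EOS loses the EOS assessment: usable post-baseline marrows fall from 3 to 2 for a Cohort 1 completer, and from 2 to 1 in Cohorts 3/3χ and 4/4χ.

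The downside is that a genuine late IMG-7289 response first seen after new therapy starts would appear only in the listing. With the 4–5 day half-life in Protocol 3.7, plasma drug 28 days after last dose is 0.5^(28/4) = 0.8% to 0.5^(28/5) = 2.1% of its level at last dose. Inhibition is irreversible, however, so a late effect cannot be excluded, and the separate listing keeps it visible.
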